Stratum 1 dosing will start with a full dose of nivolumab 3 mg/kg (dose level 1), and one dose de-escalation is allowed; after evaluating dosing for single agent nivolumab then participants will be treated with 240mg of nivolumab and 1mg/kg of ipilimumab will be added to evaluate combination therapy (dose level 2) with one dose de-escalation allowed. No intra-participant dose escalations will be allowed. The safety evaluation period is 6 weeks at a given dose level. Stratum 2 dosing will begin at the single agent therapy maximum tolerated dose (MTD) for Stratum 1 (dose level 1 or -1). Stratum 2 will not be allowed to escalate beyond the MTD for Stratum 1. Only 1 dose de-escalation will be allowed.

The study treatment consists of up to 46 intravenous (IV) infusions of nivolumab on Day 1 of each 2-week cycle for the dose level -1 and 1 cohorts. For dose level 2, IV infusions of nivolumab are given on Day 1 of each 2-week cycle and ipilimumab on Day 1 every 6 weeks, i.e., every third cycle (cycles 1, 4, 7, etc.). For dose level -2, IV infusions of nivolumab are given on day 1 of each 2-week cycle, and ipilimumab

is given on day 1 every 12 weeks, i.e., every sixth cycle (cycles 1, 7, 13, etc.). Participants with an overall response of stable disease (SD), partial response (PR), complete response (CR), or unconfirmed progressive disease (PD) at Week 8 will continue treatment (Refer to Section 9.1 for Response Evaluation Criteria in Solid Tumors (RECIST) Criteria for up to 84 weeks, (42 IV infusions of nivolumab every 2 weeks, see the table below for the ipilimumab schedule if on dose level 2 or -2).

Dose Level	Nivolumab* q2 wk (46 doses)	Ipilimumab**
-1	1mg/kg	-
1	3mg/kg	-
2	240mg	1mg/kg q 6 wk(16 doses)(day 1 of nivolumab cycles 1, 4, 7, 10, 13, 16, 19, 22, 25, 28, 31, 34, 37, 40, 43, and 46)
-2	1mg/kg	1mg/kg q 12 wk (8 doses)(day 1 of nivolumab cycles 1, 7, 13, 19, 25, 31, 37, and 43)

^{*} Treatment will continue until documented disease progression, discontinuation due to toxicity, withdrawal of consent or end of study, up to 46 doses of nivolumab.

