The combination therapy MTD will then be studied in a dose expansion cohort (12 participants) limited to only participants with Kaposi sarcoma, lung cancer, and anal cancer; CD4+ count eligibility criteria in the expansion cohort will be determined after reviewing results from Strata 1 and 2. If the MTDs differ between the two strata, expansion cohorts of six participants each will be enrolled. The study treatment consists of 12 IV infusions of nivolumab, 240 mg, on Day 1 of each 2-week cycle and ipilimumab on Day 1 every 6 weeks with four total ipilimumab doses, i.e., every third cycle (cycles 1, 4, 7, 10). After completion of the 12th cycle of nivolumab, the nivolumab dose will change to a flat dose of 480mg, on Day 1 of each 4-week cycle without ipilimumab. Participants with an overall response of SD, PR, CR, or unconfirmed PD at Week 8 will continue treatment (Refer to Section 9.1 for RECIST Criteria) for up to 84 weeks.

A single agent expansion cohort of 24 participants with solid tumors, excluding those histologies not known to respond to single agent nivolumab (i.e., pancreas, prostate, and microsatellite stable [MSS] colorectal cancer) and with CD4 count above 200 will receive single agent nivolumab at 240mg administered every 2 weeks for up to 46

^{**} After evaluating single agent nivolumab dosing, the next dose level will be 2 if dose level 1 is the MTD for single agent nivolumab and dose level -2 if dose level -1 is the single agent MTD. It is also possible to de-escalate from dose level 2 to -2.

doses, or until disease progression, toxicity, study termination, or study withdrawal.

Another single agent cohort of 12 participants with relapsed refractory HIV-associated cHL and with CD4 counts ≥ 100/mm³, will also be treated with single agent nivolumab at a flat dose of 240mg administered every 2 weeks for 46 doses or until disease progression, toxicity, study termination, or study withdrawal (See Section 9.3 for the 2017 response evaluation criteria in lymphoma (RECIL) Criteria for evaluation of measurable disease in HIV-cHL and Section 4.7 and 4.9 for study duration and criteria for removal from study). Participants with an overall response of SD, PR, CR, or unconfirmed PD at Week 8 will continue treatment. Of note, this dose showed no dose-limiting toxicity (DLT) in this trial and is the current FDA approved dosing regimen for non-HIV classical Hodgkin lymphoma.

Duration: Maximum of 92 weeks of treatment

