 - To evaluate the effects of single agent nivolumab, and the combination of ipilimumab and nivolumab on herpesvirus specific CD8 and CD4 T cells in PBMC.
 - In cases of Kaposi sarcoma, to evaluate the effects of single agent nivolumab, and the combination of ipilimumab and nivolumab on viral transcription in tumor biopsies, when feasible.
 - In cases of anal cancer, to evaluate the effects of single agent nivolumab, and the combination of ipilimumab and nivolumab on HPV types in anal swabs, when feasible.
- 3. Understand the response of HIV to agent.
 - To evaluate the effects of single agent nivolumab, and the combination of ipilimumab and nivolumab on latent HIV loads in PBMC using outgrowth assay.
 - To evaluate the effects of single agent nivolumab, and the combination of ipilimumab and nivolumab on HIV reactive T cells.

PROTOCOL SCHEMA

Abbreviations: DL= dose level; MTD = Maximum Tolerated Dose.

All participants will receive up to 92 weeks of protocol treatment if the participant has stable disease (SD), partial response (PR), complete response (CR), or unconfirmed progressive disease (PD). Dose levels and de-escalation schedules are provided on the following page.

- * If combination therapy MTD differs in Stratum 1 and Stratum 2, dose expansion will occur at Stratum 1 Dose in participants with CD4 count > 200/mm³.
- ** If the MTDs differ between the two strata, expansion cohorts of 18 and 6 participants respectively will be enrolled.

Dose De-Escalation Schedule for Stratum 1 and Stratum 2		
Dose Level	Nivolumab* q2 wk x 46 doses	Ipilimumab**
Level -1	lmg/kg	-
Level 1	3mg/kg	-
Level 2	240mg	1mg/kg q 6 wk x 16 doses (day 1 of nivolumab cycles 1, 4, 7, 10, 13, 16, 19, 22, 25, 28, 31, 34, 37, 40, 43, and 46)
Level -2	lmg/kg	1mg/kg q 12 wk x 8 doses (day 1 of nivolumab cycles 1, 7, 13, 19, 25, 31, 37, and 43)

^{*}Doses are stated as exact dose in units (e.g., mg/m², mcg/kg, etc.) rather than as a percentage.

NOTE: After evaluating single agent nivolumab dosing, the next dose level will be 2 if dose level 1 is the MTD for single agent nivolumab, and dose level -2 if dose level -1 is the single agent MTD. It is also possible to de-escalate from dose level 2 to -2. Stratum 2 participants will not be allowed to escalate beyond the MTD for Stratum 1; one dose level de-escalation of the nivolumab and ipilimumab combination or to single agent nivolumab will be allowed based on the doses in the schema in the treatment plan.

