4.2.3 Expansion Cohort in Solid Tumors and Lymphoma

An additional 24 participants with incurable solid tumors will be treated at the MTD, according to the treatment schedule defined above for each stratum. If the MTDs differ between the two strata, expansion cohorts of six participants each will be enrolled.

Another 24 participants with incurable solid tumors will be treated at single agent nivolumab 240 mg every 2 weeks. Only those histologies that are not known to respond to single agent nivolumab will be excluded (i.e., pancreas, prostate, MSS colorectal cancer, unless results from another clinical trial showing non-response in another tumor type become available in the future).

Participants with HL will be treated at the FDA approved flat dose of 240mg given every 2 weeks.

Participants with an overall response of SD, PR, CR, or unconfirmed PD at the end of the first four cycles of nivolumab will continue treatment for up to a total of 46 cycles of nivolumab (with ipilimumab if receiving dose level 2 or -2) (refer to Section 9.1 for RECIST Criteria and Section 9.3 for the 2017 response evaluation criteria in lymphoma (RECIL) Criteria for evaluating measurable disease in HIV-cHL).

Participants with a confirmed PD will discontinue the study drugs.

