4.3.4 Expansion cohorts

For the solid tumor expansion cohort, a dose of 240 mg of single agent nivolumab will be administered every 2 weeks for 46 doses as described above, as a 60-minute IV infusion. Inclusion criteria for CD4 count will be managed as noted in Section 4.1.

1 nivolumab cycle = 14 days

A maximum of 46 cycles of nivolumab will be given every 2 weeks. If the combination is tolerated, ipilimumab will be given according to the treatment instructions for dose level 2 or -2 as above, depending on the MTD for that stratum, in a separate solid tumor expansion cohort.

For the combination solid tumor expansion cohort, the dosing will be 12 intravenous (IV) infusions of nivolumab, 240 mg, on day 1 of each 2-week cycle and ipilimumab on day 1 every 6 weeks with four total ipilumimab cycles, i.e., every third cycle (cycles 1, 4, 7, 10). After completion of the 12th cycle of nivolumab, the nivolumab dose will change to a flat dose of 480 mg, on day 1 of

each 4-week cycle without ipilimumab. Participants with an overall response of SD, PR, CR, or unconfirmed PD at week 8 will continue treatment (Refer to Section 9.1 for RECIST Criteria) for up to 84 weeks. For participants with HIV-cHL, single agent nivolumab will be given as a flat dose of 240 mg every 2 weeks as described in Section 4.3.1.

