4.6.4 Precautions

Combination therapy may result in unexpected toxicity especially in novel combinations with other immune modifying agents. A striking example in macaques is presented in Vaccari, *et al.* 2012.

Please note that while unproven, there is a suggestion that autoimmune events, including hepatitis, may occur more frequently at sites of metastases or prior injury.

Caution is advised when considering treatment with high dose IL-2 in participants who have previously been administered ipilimumab, particularly in participants who experienced ipilimumab-related diarrhea/colitis. Colonoscopy or sigmoidoscopy with biopsy may be advisable prior to IL-2 administration once the participant is no longer receiving ipilimumab.

Participants who have received ipilimumab may potentially develop autoimmune disease with subsequent therapy including the appearance of colitis, hypophysitis, or adrenal insufficiency.

4.7 **Duration of Therapy**

In the absence of treatment delays due to AE(s), treatment may continue 92 weeks of nivolumab (with ipilimumab, if receiving dose level 2 or -2) until one of the following criteria applies:

• The development of progression (confirmed PD by RECIST Criteria or PD by the KS evaluation criteria in Section 9.2 or per Section 9.3, utilizing the consensus RECIL (2017). Participants will remain on study treatment until progression is confirmed,

Pregnancy

- All WOCBP should be instructed to contact the investigator immediately if they suspect they might be pregnant (e.g., missed, or late menstrual period) at any time during study participation. Institutional policy and local regulations should determine the frequency of on study pregnancy tests for WOCBP enrolled in the study.
- o The investigator must immediately notify CTEP in the event of a confirmed pregnancy in a study participant.
- Intercurrent illness that prevents further administration of treatment.
- Unacceptable AE(s) which include the following (see also Section 6.0 and specific algorithms in Appendix X):
 - o Any grade 4 events except as noted below.
 - o Grade 3 drug-related autoimmune or inflammatory events including uveitis, pneumonitis, diarrhea, colitis, neurologic AEs, hypersensitivity reaction, or infusion reaction of any duration requires discontinuation except as noted below:
 - o Any other grade 3 non-skin, drug-related AE lasting >7 days including fatigue.

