8.6 Combination Therapy Solid Tumor Expansion Cohort: Cycle 5-23 Day 1

Unless noted otherwise below, the evaluations may be performed up to three days prior to treatment.

- 8.6.1 Review of medical history since last visit
- 8.6.2 Physical examination (vital signs, weight, performance status)
- 8.6.3 Review of changes in concurrent medications
- 8.6.4 Laboratory studies (as defined in Section 8.1.5)
 - a) CBC with differential and platelet count within 2 days prior to treatment
 - b) Serum chemistries Serum amylase and lipase
 - c) Serum or urine pregnancy test for WOCBP at Cycle 5 Day 1 and every 12 weeks thereafter
 - d) HIV viral load and CD4/CD8 count at Cycle 5 Day 1 and every 12 weeks thereafter: Viral load studies will be performed using an assay with a limit of detection of 75 copies/ml or less. Repeat Hepatitis B antigen and/or Hepatitis C antibody if positive at baseline.
 - e) Immunologic labs at Cycle 5 Day 1 and every 12 weeks thereafter after consisting of: rheumatoid factor, C-reactive protein, ANA, SPEP, immunoglobulins, and FLC.
 - f) Endocrine labs at Cycle 5 Day 1 and every 12 weeks thereafter consisting of: TSH, free T4, TPO, morning ACTH, and morning cortisol if ACTH is abnormal

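### The combination-therapy expansion cohort's visit listings stop at cycle 22 or 23, but the 92-week treatment maximum implies 29 cycles and Section 4.2.3 allows 46

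*Combined protocol and SAP*

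**What the plan says.** **Regimen.** Section 4.3.4 says of the combination solid tumor expansion cohort that "the dosing will be 12 intravenous (IV) infusions of nivolumab, 240 mg, on day 1 of each 2-week cycle". After cycle 12, "the nivolumab dose will change to a flat dose of 480 mg", given every four weeks without ipilimumab. The synopsis describes the same regimen. Both add that participants without confirmed progression at week 8 continue for up to 84 weeks.

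**Maximum duration.** The synopsis states "Maximum of 92 weeks of treatment". The schema states "All participants will receive up to 92 weeks of protocol treatment", subject to disease status. Section 4.7 states "treatment may continue 92 weeks of nivolumab (with ipilimumab, if receiving dose level 2 or -2").

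**Cycle cap.** Section 4.2.3 covers the solid tumor and lymphoma expansion cohorts together. It says participants without confirmed progression after four cycles "will continue treatment for up to a total of 46 cycles of nivolumab", and it expressly includes those on ipilimumab at dose level 2 or -2.

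**Visit listings.** Section 8.6 is headed "Combination Therapy Solid Tumor Expansion Cohort: Cycle 5-23 Day 1". In the Appendix I schedule of evaluations for this cohort, the last on-treatment column covers cycles 14 to 22, and the next column is off study.

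**The concern.** The regimen, the maximum duration, the cycle cap and the two visit listings should all describe the same period of treatment. They do not, and the two visit listings differ from each other by one cycle.

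Two things are at stake. First, some on-treatment assessments for this cohort are scheduled through Sections 8.6.1 to 8.6.3 and the matching Appendix I rows: interval history, physical examination with vital signs, weight and performance status, and review of concurrent medication. Once the listing ends, these have no stated visit. Performance status matters because Sections 4.2.1 and 5.1 make continued treatment depend on an ECOG score of 2 or less at response visits.

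Second, a site working from the calendar and a site working from Section 4.7 could treat for different lengths of time. The primary objective in Section 1.1 covers safety and feasibility in the expansion cohorts, so uneven exposure and uneven on-treatment visits would feed into its data.

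**Working it through.** **Inputs.** Maximum of 92 weeks (synopsis, schema, Section 4.7). 12 two-week cycles, then four-week cycles (synopsis, Section 4.3.4). Last listed cycle 23 (Section 8.6) or 22 (Appendix I). Cap of 46 cycles (Section 4.2.3).

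**1. The plan's own figure.** On a two-weekly schedule, 46 × 2 = 92 weeks. The synopsis describes continuation after week 8 in the de-escalation cohorts as "for up to 84 weeks, (42 IV infusions of nivolumab every 2 weeks"; 42 × 2 = 84, and 8 + 84 = 92. So the 92 weeks reproduces exactly for cohorts dosed every two weeks throughout.

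**2. Cycles needed in this cohort.** The first 12 cycles take 12 × 2 = 24 weeks. For a total of T weeks, cycles = 12 + (T − 24)/4.
- T = 92: 12 + 68/4 = 29 cycles.
- T = 84, if that figure is a total: 12 + 60/4 = 27 cycles.

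**3. Where each stated end point falls.** For n of 13 or more, cycle n starts at elapsed week 24 + 4(n − 13) and ends four weeks later.

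| Source | Last cycle | Day 1 (elapsed week) | Ends (week) |
|---|---|---|---|
| Appendix I | 22 | 60 | 64 |
| Section 8.6 | 23 | 64 | 68 |
| 84 weeks as a total | 27 | 80 | 84 |
| 92 weeks | 29 | 88 | 92 |
| Section 4.2.3 | 46 | 156 | 160 |

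**4. Permitted treatment with no listed visit.**
- Against 92 weeks: 92 − 64 = 28 weeks (cycles 23 to 29, seven visits) under Appendix I; 92 − 68 = 24 weeks (cycles 24 to 29, six visits) under Section 8.6.
- Against 84 weeks: 84 − 64 = 20 weeks and 84 − 68 = 16 weeks.

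**5. Does another reading remove the conflict?** The calendar groups cycles 5 to 13 together, which might suggest 13 two-week cycles. That moves the ends of cycles 22 and 23 to weeks 62 and 66 and makes 92 weeks equal 13 + 66/4 = 29.5 cycles, so it does not help. Also 92/4 = 23, so the Section 8.6 heading may have treated every cycle as four weeks long. That is inference; the protocol does not say so.

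**6. What continues without a listed visit.** These rules carry no last cycle:
- Local laboratory evaluation reviewed before each dose (Section 4.3.5), with blood count and chemistry timing tied to each infusion (footnotes a, b, d and e of this cohort's calendar).
- Viral load and immunologic tests every 12 weeks until off study (footnotes f and g).
- Imaging and response assessment every 12 weeks (Section 8.6.7, Sections 9.0 and 9.1, footnote j). Counted from week 8, these fall at weeks 8, 20, 32, 44, 56, 68, 80 and 92, so the last three lie at or beyond the end of the listed cycles.
- Adverse event assessment until 90 days after the last dose (Section 8.7, footnote k).
- Kaposi sarcoma assessment every four weeks during participation (footnote l).

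**The case against.** The strongest objection is that treatment duration itself is clear. The synopsis, schema and Section 4.7 all say 92 weeks, and the 84 weeks is most naturally the time after week 8. A heading over a list of visits does not set treatment length. The 46 cycles in Section 4.2.3 is right for the single-agent and lymphoma cohorts that share the paragraph, and Section 4.3.4 gives the specific schedule for this one. Most of this stands, and it makes the 27-cycle reading the less supported one. It does not explain why two visit listings for one cohort end at different cycles, both short of 29. Nor does Section 4.2.3 set this cohort apart: it includes participants on ipilimumab by name.

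A reader might infer that the later weeks have no safety or response assessment at all. The documents do not support that, because the rules in step 6 still apply. The remaining gap can be narrowed a little further. Footnote c provides for vital signs around infusions from cycle 5 onward with no end. Section 4.2 mentions examination at two-weekly follow-up to 92 weeks, but it is written for the de-escalation cohorts and does not fit four-week cycles.

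A reader might also infer that duration of response is cut off at cycle 22 or 23. Section 9.1.5 runs it to documented progression, and Section 10.4.1 only describes it. The dose-limiting toxicity decision uses a 6-week window and is unaffected.

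**Conclusion.** The inconsistency is real and lies in current operative text. For this cohort the documents give end points of cycle 22 (week 64), cycle 23 (week 68), 92 weeks (29 cycles) and 46 cycles (week 160). On the 92-week maximum, 24 to 28 weeks of permitted treatment, or six to seven Day 1 visits per participant who stays on treatment, have no listed visit. On the less supported 84-week total it is 16 to 20 weeks.

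The consequence is limited to the items that rest on the listing: physical examination with its vital signs, weight and performance status, interval history, and concurrent-medication review. Laboratory, response and adverse event data remain scheduled.

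The figures assume that the switch to four-week cycles comes after cycle 12, as Section 4.3.4 states, and that there are no dose delays. The column headings of the Appendix I table are partly garbled in the text available, so the one-cycle difference between 22 and 23 is less certain than the shortfall against 29, which holds on either number.

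**What to change.** Reconcile the synopsis, schema, Sections 4.2.3, 4.3.4, 4.7 and 8.6 and the Appendix I calendar on one maximum duration and one cycle count for the combination-therapy expansion cohort. Which duration and count apply is for the sponsor to decide. State whether the 84 weeks is counted after week 8 or is a total. In Section 4.2.3, separate this cohort from the 46-cycle statement. Then run the Section 8.6 heading and the Appendix I columns to the agreed last cycle, so that examination, performance status, history and medication review have a visit for as long as treatment is permitted.

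The cost is amendment wording and a table update. No new type of assessment is needed. If the agreed maximum exceeds the current listing, the added visits fall on days when participants already attend for dosing.

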8.6.5 AE assessment

Biological sample submissions for correlative studies. Samples will be collected as defined in Section 8.1.10, unless otherwise noted.

- a) Collect two 6 ml red top tubes for assessment of circulating levels of proinflammatory molecules before cycle 5. Collection, shipping, and storage methods are described in Appendix XV.
- b) Collect anal swabs before cycle 5 as described in Appendix XVII (optional for anal cancer cases only, with participant consent).
- c) Blood draw: Five 8.5mL ACD tubes for assays (HIV DNA, HIV RNA, SCA, and Pheno/ICS) with hematocrit ≥ 25, to be collected pre-dose on Day 1, post-dose on Day 1, and on Day 8 of Cycles 7, 10, (Appendix XIV). The pre-dose sample and the Day 1 Cycle 1 sample must be drawn on different calendar days and should be collected at least 12 hours apart. The post-dose sample must be

drawn between 12 and 36 hours after the infusion has been completed. Every effort should be made to process samples for viable PBMC and plasma on site within 6 hours of collection. The samples will be shipped to the AMC Biorepository via priority overnight service for processing if this cannot occur on site.

- d) Blood draw: Twelve 8.5mL ACD tubes for assays (latent reservoir and VOA) for all participants who consent to this optional draw with hematocrit ≥ 25 to be collected **on day 1 of cycle 15.** These tubes will be shipped directly to the AMC Biorepository for processing (Appendix XVI).
- e) If a participant has not consented to the HIV latent reservoir testing blood draw, two 8.5 yellow top tubes will be collected for herpesvirus load and latent virus studies on day 1 of cycle 15 (Appendix XIV and Appendix XVI).
- 8.6.7 Radiologic assessment of response before cycle 5, and thereafter every 12 weeks. All imaging studies or CT scans should be performed in an identical way to the baseline scan with the same scanner, same scan direction, and consistent arm pointing. Confirmatory scans should also be obtained 4 weeks following initial documentation of objective response. If tumor flare is suspected, the participant must undergo a second scan within a month of the first scan and the case must be discussed with the principal investigator. If progression is documented at that time, participant must come off study. If a scheduled response assessment is missed, an assessment must be completed and documented prior to drug administration for the next cycle.

